12.3.1 Primary Efficacy Endpoint

The primary efficacy endpoint is the actual reduction in weekly PS volume from baseline to Week 24. Baseline weekly PS volume is defined as the PS volume received during the 7-day period prior to Visit 1 (Day 1), i.e. during the stabilization phase. The Week 1, 2, 4, 8, 12, 16, 20, and 24 weekly PS volume is defined as the PS volume received during the 7-day period prior to these visits.

The primary analysis uses a restricted maximum likelihood (REML)-based repeated-measures approach to compare treatment groups with respect to the mean change from baseline in weekly

PS volume at Week 24. The model will use weekly PS volume assessments at Week 1, 2, 4, 8, 12, 16, 20, and 24, and will include the covariates for treatment group, baseline weekly PS volume, visit (categorical variable), stratification factor (weekly PS volume requirements <12 L/week versus >12 L/week), and visit-by-treatment group interaction. Variance estimation is based on an unstructured covariance matrix, which does not presume a particular correlation structure for repeated weekly PS volume measurements within patients over time. The primary comparison is the difference in the reduction in weekly PS volume from baseline to Week 24 between each glepaglutide treatment group versus placebo.

Following the *Treatment Policy* estimand strategy, missing values will be imputed using multiple imputation methods. For the primary analysis, a *Copy Reference (CR)* approach is used with placebo treatment as reference, while for sensitivity analyses, a *Jump to Reference (J2R)* and a *Copy Incremental from Reference (CIR)* approaches will be applied. Details are described in [Section 12.6](#) and in the SAP.

The Copy Reference approach is justified as the trophic effects on the intestines mediated by glepaglutide would take weeks to abate after treatment withdrawal. A longitudinal growth of the remaining intestines could also have occurred after prolonged therapy and such modifications would not be expected to return fully to the baseline condition. Other effects of GLP-2 agonism, like reduced fluid secretion from the upper part of the GI tract and effects on reducing motility would however be expected to return to the baseline conditions when treatment is withdrawn.

As a supplementary analysis, the analysis will be repeated using the Per-protocol Analysis Set.

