3. ENDPOINTS

3.1. PRIMARY EFFICACY ENDPOINT

The primary efficacy endpoint is the change in actual weekly PS volume from baseline to Week 24.

Baseline actual weekly PS volume is defined as the actual PS volume derived from a valid 7-day period prior to Visit 1 (Day 1), i.e. during the stabilization phase. The actual weekly PS volume at Weeks 1, 2, 4, 8, 12, 16, 20, and 24 will be derived as the actual weekly PS volume received during the valid 7-day period prior to the visit. The source for the derivation will be the PS volumes recorded by the patients in the eDiary; for details on the derivation of actual weekly PS volume see Appendix A. Supportive analyses will be performed to explore the robustness of the primary analysis with regard to the algorithm for deriving the primary endpoint, see 3.1.4.

Following the treatment policy strategy, for patients who prematurely discontinue treatment but complete the trial providing eDiary information up-to Week 24, the actual weekly PS volume derived at Week 24 after treatment discontinuation will be included in the primary analysis of the primary efficacy endpoint. For patients who prematurely discontinue treatment and did not complete the trial, having an end of treatment visit (Visit 10) prior to Week 24 - 14 days (169-14 days), the derived actual weekly PS volume at the end of treatment visit will not be carried forward to represent Week 24. Instead 1) the value at Week 24 will be set to missing and imputed with the multiple imputation method described below for the primary analysis of the primary endpoint and 2) the derived actual weekly PS volume at the end of treatment visit will be re-allocated to a previous visit and used in the MMRM model. If, when re-allocating the end of treatment visit there is already a visit in the same time window, then the value of the scheduled visit will be used in the analysis, not the re-allocated end of treatment value.

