The primary analysis uses a restricted maximum likelihood (REML)–based repeated-measures approach to compare treatment groups with respect to the mean change from baseline in actual weekly PS volume at Week 24. The model will use actual weekly PS volume assessments at Weeks 1, 2, 4, 8, 12, 16, 20, and 24 as an independent variable, and will include the covariates of treatment group, baseline actual weekly PS volume, visit (categorical variable), stratification factor (weekly PS volume requirements <12 L/week versus \geq 12 L/week), and visit-by-treatment group interaction. Variance estimation is based on an unstructured covariance matrix, which does not presume a particular correlation structure for repeated weekly PS volume measurements within patients over time. The primary comparisons are the contrasts (differences in least squares means) between the glepaglutide treatment groups and the placebo group at the Week 24 visit in this mixed-effects model for repeated measures (MMRM).

Missing values will be imputed using multiple imputation methods. For the primary analysis, a Copy Reference (CR) approach is used (main estimator), while for sensitivity analyses, a Jump to Reference (J2R) approach (sensitivity estimator 1) and a Copy Incremental from Reference (CIR) approach (sensitivity estimator 2) will be applied. Details are described in 5.3.1 below.

The Copy Reference approach is justified as the trophic effects on the intestines mediated by glepaglutide would take weeks to abate after treatment withdrawal. A longitudinal growth of the remaining intestines could also have occurred after prolonged therapy, and such modifications would not be expected to fully return to the baseline condition. Other effects of GLP-2 agonism-like reduced fluid secretion from the upper part of the GI tract and effects on reducing motility would, however, be expected to return to the baseline conditions when treatment is withdrawn.

As an additional sensitivity analysis (sensitivity estimator 3), the actual weekly PS volume will be derived using a valid 14-day period prior to the visit. For details on the derivation of actual weekly PS volume within a 14-day period, see Appendix A. This endpoint will be analyzed in the same manner as for the primary analysis for the primary endpoint.

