In addition, a supplementary estimand will be included using a 'treatment policy strategy' assessing the treatment effect of

• Difference in percentage of clinical response between glepaglutide treatment group and placebo in the SBS population, regardless of whether treatment is discontinued.

Response status will be derived from the CR-imputed data sets generated from the multiple imputation approach described for the primary estimand (main estimator) of the primary efficacy endpoint. The difference will be analysed in the same way as the primary analysis of first key secondary efficacy endpoint. The test statistics based on the MI will be combined by applying Rubin's rule after Wilson-Hilferty transformation (Wilson et al 1931).

25 August 2022

To get an overview of the different estimands and estimators for the binary key secondary efficacy endpoints, and how missing data will be handled, please see Table 6.

Second key secondary efficacy endpoint: Reduction in days on $PS \ge 1$ day/week from baseline to Week 24

The same estimands (main estimators) and sensitivity estimator will be investigated, as for the first key secondary efficacy endpoint (see Table 6). The same analysis method will be applied as well.

Primary 'composite' estimand for the second key secondary efficacy endpoint

• Difference in percentage of reduction in days on $PS \ge 1$ day/week from baseline to Week 24 without treatment discontinuation between glepaglutide treatment group and placebo in the SBS population.

Supplementary 'treatment policy' estimand for the second key secondary efficacy endpoint

• Difference in percentage of reduction in days on $PS \ge 1$ day/week from baseline to Week 24 between glepaglutide treatment group and placebo in the SBS population, regardless of whether treatment is discontinued.

For the supplementary estimand, response status is derived using the same MI model as for primary analysis of primary efficacy endpoint with the number of PS days as dependent variable.

Third key secondary efficacy endpoint: Change in actual weekly PS volume from baseline to Week 12

The same estimands (main estimators) and sensitivity estimators will be investigated, as for the primary efficacy endpoint (see Table 3). The same analysis method will be applied as well (see 3.1).

Primary 'treatment policy' estimand for the third key secondary efficacy endpoint

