5.3. MISSING DATA AND DATA HANDLING RULES

Every effort will be made to collect all data at specified time points, according to the schedule of trial events. Reasons for withdrawal from the trial will be recorded on the eCRF.

For actual weekly PS volume, a detailed algorithm is included in Appendix A. In brief, for each visit, the actual weekly PS volume will be derived by using a valid 7-day period closest to the visit where

1. the actual weekly PS volume accounted for \geq 90% of prescribed weekly PS volume

or

2. there is at least one actual PS volume accounted for by the patient in the eDiary for each day in the valid 7-day period

For all post-baseline visits, the 7-day period is allowed to start up to 14 days before a visit, provided that it does not start before the previous visit. For baseline visits, the 7-day period is allowed to start up to 30 days before the baseline visit, provided that it does not start before the latest optimization visit. The Day 3 and Week 1 visits are not included in the calculations.

Note that, if the last PS prescription during the treatment period has been stopped more than 7 days prior to a visit, and there are no entries of actual PS volumes recorded by the patient in the eDiary within 7-days prior to this visit then the actual weekly PS volume will be set to zero.

The efficacy endpoints will be missing at visits, where no valid 7-days period can be found based on the above algorithm.

Any missing data during the trial prior to trial completion or discontinuation will remain as missing at that time point. However, several multiple imputation methods will be used to impute missing data for the primary efficacy endpoint as well as for the key secondary efficacy endpoints. See 5.3.1 for details of the multiple imputation method.

Imputation rules for the handling of missing data for PROs and health economic assessments will follow rules per each assessment manual.

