The remaining, monotone missing data for all patients who discontinue the trial prematurely will be imputed using sequential regression multiple imputation model estimated based on data from the placebo arm only. Each sequential regression model (i.e., for imputation of values at a given time point) will include explanatory variables (treatment group, visit (categorical variable), stratification factor (weekly PS volume requirements <12 L/week versus \geq 12 L/week)), and all previous (Baseline weekly PS volume, Visit at Weeks 1, 2, 4, 8, 12, 16, 20, and 24) values of actual weekly PS volume. Missing values at a given time point in placebo and glepaglutide arms will be imputed from the same imputation model, conditional on patient values observed or imputed at previous time points. No rounding or range restrictions will be applied to imputed continuous values.

Imputed data will consist of 100 imputed datasets. A different and separate random seed number will be used for the partial imputation with the MCMC method, and for the sequential regression multiple imputation. Those random seed numbers are specified in Table 7 below.

	Random seed for imputing monotone missingness (if applicable)	Random seed for imputation of remaining data	Number of imputations
Primary imputation	mary imputation 2125		100

Table 7 Random seeds and number of imputations

Each of the 100 imputed datasets will be analyzed using the following analysis method. Change in actual PS volume from baseline to each post-baseline visit will be calculated based on observed and imputed data. Treatment group comparison at Week 24 will be based on the least squares mean (LSM) difference between glepaglutide groups and placebo in change from 25 August 2022 Confidential Page 34 of 65

baseline in actual PS volume estimated by the analysis model in each of the imputed datasets. Results from analysis of each imputed dataset, i.e., LSM treatment differences and their standard errors, will be combined using Rubin's imputation rules to produce a pooled LSM estimate of treatment difference, its 95% confidence interval, and a pooled p-value for the test of null hypothesis of no treatment effect.

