APPENDIX A. CALCULATION OF PRESCRIBED AND ACTUAL WEEKLY PS VOLUME

Prescribed weekly PS volume based on a 7-day period

The prescribed weekly PS volume (L/week) record per patient per nominal visit attended on or after Visit 1 (Day 1) will be calculated. The source is the prescribed PS volumes recorded in the eCRF by the investigator (SDTM.CM where CM.CMSCAT= 'PARENTERAL SUPPORT PRESCRIPTION').

A prescribed PS regimen consists of \geq 1'bag identifier(s)' (SDTM.CM.CMSPID). For each prescribed 'bag identifier' the volume (SDTM.CM.CMDOSE) is recorded in L/week. The prescription of a 'bag identifier' is considered current from the start date (CM.CMSDTC) until the end date (CM.CMENDTC) or until the end of trial if the last prescription end date is not available, hereafter referred to as a prescription period.

A prescription period might cover several visits. A PS prescription can be updated at the scheduled visits, but also in between visits at the discretion of the investigator.

If the end date of a current prescription period is the same as the start date of the next prescription period, the end date of the current period is set to the end date minus one day to avoid overlap.

The prescribed volume (AVAL) is derived as the sum of the prescribed volumes during the 7day period just prior to the visit divided by 7 (to account for the volumes being recorded in L/week), i.e. the period is defined from the visit date minus 1 to the visit date minus 7. Hereafter referred to as the *prescribed volume*.

Note that, if the last PS prescription during the treatment period has been stopped more than 7 days prior to a visit, the prescribed weekly PS volume will be set to zero at the relevant visit.

Actual weekly PS volume based on a valid 7-day period

An actual weekly PS volume (L/week) record per patient per nominal visit attended on or after Visit 1 (Day 1) will be derived, with the exception of visits Day 3 and Week 1 which will not be included in the ADaM dataset (see steps below).

The source is the actual PS volume records entered into the eDiary by the patient (SDTM.ZP), hereafter referred to as volume records.

The actual weekly PS volume (AVAL) is derived as the sum of the volume records (ZP.ZPSTRESN) in a valid 7-day period prior to the relevant visit. Hereafter referred to as the *actual volume*.

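### SAP Appendix A leaves Week 1 out of the PS volume dataset, against the eight-visit primary model and its own Week 1 window rule; it also ties each value to an undefined 'attended' visit

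*SAP*

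**What the plan says.** **Week 1 is required.** SAP 3.1 states: "The actual weekly PS volume at Weeks 1, 2, 4, 8, 12, 16, 20, and 24 will be derived". Of the primary analysis it says: "The model will use actual weekly PS volume assessments at Weeks 1, 2, 4, 8, 12, 16, 20, and 24". The sequential imputation model in SAP 5.3.1 lists the same visits: "Baseline weekly PS volume, Visit at Weeks 1, 2, 4, 8, 12, 16, 20, and 24". Protocol 12.3.1 agrees ("The model will use weekly PS volume assessments at Week 1, 2, 4, 8, 12, 16, 20, and 24"), and protocol 12.6 has the same imputation list. SAP 3.2 applies the method of section 3.1 to the Week 12 key secondary endpoint.

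**Week 1 is excluded.** The opening of the actual-volume part of Appendix A derives a record per visit "with the exception of visits Day 3 and Week 1 which will not be included in the ADaM dataset". SAP 5.3 adds: "The Day 3 and Week 1 visits are not included in the calculations".

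**Week 1 is given a rule.** Step 2 of the same part of Appendix A lets the Week 1 window start before the Day 3 or baseline visit. It names only Day 3 as lying outside the dataset. Table 5 in SAP 3.1.4 repeats the Week 1 and Week 2 exemption for the main estimator.

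**Attendance.** Appendix A derives a value only for an attended nominal visit and counts each window back from the visit date. Neither document defines the word. SAP 3.1.3 plans no COVID-19 sensitivity analysis, on the ground that diary PS volume does not depend on coming to the clinic.

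**The concern.** The derivation rule for the primary endpoint conflicts with the model it feeds. Read literally, the opening of Appendix A gives both models seven post-baseline visits, and the early treatment estimate that Week 1 was meant to supply does not exist. SAP section 12 has two programmers work independently from the specifications. With this text, one could build a seven-visit dataset and the other an eight-visit dataset, and each could cite Appendix A.

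The attendance wording matters less often but reaches Week 24 itself. Take a patient still in the trial, with a valid Week 24 diary period but no Week 24 visit in any form. That patient would have no derived value. Table 3 would then send the primary endpoint to placebo-based imputation, and SAP 3.2 would score the Week 24 binary endpoints as non-response. A treatment-policy estimand would use the recorded value, and protocol 7.5 asks sites to make a special effort to obtain it.

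**Working it through.** **1. The texts side by side.**

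| Place | Week 1 |
|---|---|
| SAP 3.1, derivation and model | derived and used |
| SAP 5.3.1; protocol 12.3.1 and 12.6 | used |
| SAP Appendix A step 2; Table 5 | given a window rule |
| SAP Appendix A, opening | not in the dataset |
| SAP 5.3 | not in the calculations |

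SAP section 8, which lists changes from the protocol, does not mention dropping Week 1. The version 6.0 log in SAP section 9, used here only for intent, says Week 1 was added to the primary and imputation models and that the window exemption was made for that reason. An unstructured covariance has 8 × 9 / 2 = 36 parameters with eight visits and 7 × 8 / 2 = 28 with seven.

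**2. The plan's own figure.** SAP 2.6 gives 95% power for either regimen at 108 patients. With differences of 4.5 − 2.3 = 2.2 and 4.3 − 2.3 = 2.0 L/week, SD 2.62, 36 per arm, two-sided 0.025 for each comparison and correlation 0.5 from the shared placebo arm, the result is 95.8% (normal) or 95.3% (t-based). The figure is reproduced and does not depend on Week 1.

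**3. Size of the Week 1 effect.** With complete data and baseline and stratum slopes common to all visits, dropping Week 1 changes only the pooled slopes. Every later contrast therefore shifts by the same amount, Weeks 12 and 24 alike. Two simulations used 36 per arm with the arm means and SD of SAP 2.6; all other inputs are assumed.
- *First:* gamma baseline (mean 13.5, SD 7), Week 1 SD 0.3 or 1.0, adjacent-visit correlation 0.85, baseline slope at Week 24 of 0, −0.15 or −0.3; 300 trials with two contrasts each per setting. Eight-visit minus seven-visit contrast: mean within 0.005 L/week, SD 0.013 to 0.063, 95th percentile of the absolute value 0.028 to 0.129, maximum 0.27.
- *Second:* baseline mean 13, SD 6; four-week correlation 0.5, 0.8 or 0.95; 200 trials per setting. SD of the Week 24 shift 0.015 to 0.024, maximum 0.105; standard error about 0.63 with or without Week 1.

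Neither simulation included missing data, so any effect through the imputation model is not quantified.

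**4. Why SAP 5.3 needs more than a deletion.** SAP 5.3 bars a window that starts before the previous visit and does not carry the Appendix A exemption. Suppose only the words on Week 1 were deleted there.
- Week 1 visit (Days 6 to 10): the first window starts seven days earlier, which is before Day 1 for visits on Day 6 or 7. That is 2 of 5 permitted days.
- Week 2 visit (Days 12 to 18): the first window starts on Day 5 for a Day 12 visit, Day 6 for Day 13, and so on. It precedes the Week 1 visit in 5 + 4 + 3 + 2 + 1 = 15 of 5 × 7 = 35 day pairs.

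Under step 2 of Appendix A, a window that starts too early sets the value to missing and stops the search.

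**5. Attendance, illustration only.** For an active patient missing only Week 24, assume equal SDs and first-order dependence. The effect lost under Copy Reference is d24 − ρ × d20, where d is the difference from placebo. Take d24 = 2.2 and assume ρ from 0.70 to 0.95 and d20/d24 of 0.8 or 1.0.
- Smallest: 2.2 − 0.95 × 2.2 = 0.11 L/week; 0.11 / 36 = 0.003 on the arm mean.
- Largest: 2.2 − 0.70 × 1.76 = 0.97 L/week; 0.97 / 36 = 0.027 on the arm mean.
- One lost responder in an arm of 36: 1/36 = 2.8 percentage points.

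**The case against.** The strongest reply is that the SAP settles Week 1 itself. Every operative section derives it, the steps of Appendix A give it a window, and one clause is left over from an older text. A reader might infer that the eight-visit model cannot be run at all. The documents do not support that, because Appendix A's own steps derive Week 1. What stands is that the clause is still an instruction about the content of the dataset and contradicts those steps.

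The sentence in SAP 5.3 might be taken as a second firm contradiction. It is weaker than that. The section describes itself as a summary ("a detailed algorithm is included in Appendix A. In brief, for each visit"), and the sentence follows directly on the previous-visit rule, so it may mean only that Day 3 and Week 1 do not block a window.

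On attendance, a reader might infer that patients seen by phone during the pandemic lose their Week 24 value. That is unlikely: Appendix A has to except Day 3, which protocol 10.4.2 makes a phone visit, so phone visits probably count. Nor does SAP 3.1.3 promise a value without a visit; it speaks of how the diary is collected. The SAP 3.1 rule on using diary data to Week 24 covers treatment discontinuers who complete the trial, and protocol 6.4 ties completion to the end-of-treatment or Follow-up visit. That rule clashes with Appendix A only for someone who skips the former and attends the latter. Nothing in the documents shows that patients without any Week 24 contact exist.

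**Conclusion.** The Week 1 clause in Appendix A is wrong as written and should be corrected before unblinding. Its expected numerical effect is very small: a mean shift of about zero at Weeks 12 and 24, and a largest single-trial shift of 0.27 L/week in the less favourable simulation, against planned differences of 2.0 to 2.2 L/week. These sizes rest on assumed baseline distributions, correlations and slopes, and on complete data. They give no ground for calling the primary result biased. The main loss under the literal reading is the Week 1 estimate and an unambiguous dataset specification.

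The attendance point is secondary and minor. The number of affected patients is not given, so the per-patient figures are illustrations, and no loss of power or shift in the trial result can be claimed from them. Replacing an active patient's recorded value in this way would generally work against the drug. Non-response scoring applies to placebo as well, so the effect on a difference in response rates could be smaller than 2.8 points per patient.

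**What to change.** - **Appendix A, opening of the actual-volume derivation:** limit the exclusion to Day 3.
- **SAP 5.3:** replace the sentence on Day 3 and Week 1 with the content of Appendix A step 2: Day 3 is not in the dataset, the Week 1 window may start before Day 3 or baseline, and the Week 2 window may start before Week 1 or Day 3.
- **14-day derivation in Appendix A:** leave it unchanged.
- **Attendance:** state in Appendix A that a phone visit counts as attended. For a patient still in the trial with no visit held in any form, anchor the look-back on the target day (Day 169 for Week 24) and derive the value if a valid 7-day diary period exists. The in-trial condition keeps the zero-volume rule from being applied to someone who has left.

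The cost is two corrected sentences, one definition and one extra derivation branch, programmed before unblinding. No new data are needed.
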